Descriptive statistics will be provided for clinical laboratory evaluations and vital signs data. Laboratory shift tables from baseline to worst values will be presented. Abnormal physical examination findings, ECG, and echo data will be presented in by-patient listings.

Descriptive statistics will be provided for ECG interval data and presented as both actual values and changes from baseline relative to each on study evaluation and to the last evaluation on-study.

Descriptive statistics (eg, mean and standard error of the mean) for observed levels of PD parameters and the relative change from baseline will be presented for each of the postdose follow-up time points.

PK analyses will be conducted using non-compartmental methods. PK parameters including C_{max} , t_{max} , $t_{1/2\beta}$, AUC, Fe, CL/F, and V/F will be estimated. Other PK parameters may be calculated, if deemed necessary. Anti-drug antibody results will be summarized descriptively. A by-patient listing will also be provided.

Table 1: Schedule of Assessments

Study Stage	Screening	Dosing Period												Safety F/U for treatment disc ^b			
		For monthly dosing only		M1		M3		M6		M9		M12		M18 and Q6M after	M51 (EOT)	M54 (EOS/ET)	Every 3 months
Study Visit (Month)	Screening ^a	Base-line ^a		M1	M2												
Study Day	-30 to -1	-1	1	29	57	84	85	168	169	252	253	336	337	Q168D	1428	1512	Q84D
Visit Window (D)		-7		±7	±7			±7		±7		±7		±28	±28	±28	±28
Informed consent/assent	X																
Demography ^c	X																
Medical history ^d	X	X															
Inclusion/exclusion criteria	X		X														
Full physical examination		X											X			X	
Symptom-directed physical examination				X	X			X		X		X		X			X
Height ^e		X		X	X			X		X		X		X		X	X
Body weight and BMI		X		X	X			X		X		X		X		X	X
Vital signs ^f			X	X	X			X		X		X		X		X	X
12-lead ECG ^g			X					X		X		X		X	X (M24, 36, 48 only)		X
Echo		X ^h							X				X				
Pregnancy test ⁱ			X	X	X			X		X		X		X	X	X	X
Clinical laboratory assessments ^j			X	X	X			X		X		X		X		X	X

Study Stage	Screen-ing	Dosing Period												Safety F/U for treatment disc ^b			
		For monthly dosing only		M1	M2	M3	M6	M9	M12	M18 and Q6M after	M51 (EOT)	M54 (EOS/ET)	Every 3 months				
Study Visit (Month)	Screen-ing ^a	Base-line ^a		M1	M2	M3	M6	M9	M12	M18 and Q6M after	M51 (EOT)	M54 (EOS/ET)	Every 3 months				
Study Day	-30 to -1	-1	1	29	57	84	85	168	169	252	253	336	337	Q168D	1428	1512	Q84D
Visit Window (D)		-7		±7	±7		±7	±7	±7	±7	±7	±7	±28	±28	±28	±28	±28

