- Hatched columns indicate study visits to be conducted **only** for subjects who require monthly dosing.

^a Screening and Baseline visits may be combined, if possible. Assessments required prior to dosing during the screening or baseline visit in this protocol do not need to be repeated if performed in the ALN-GO1-001 protocol within the 30 days before the first dose with the exception of vital signs, ECGs, and physical examinations.

^b Patients who discontinue study drug early will be asked to return for their next scheduled visit to complete ET assessments and to complete safety follow-up visits once every 3 months, per the safety follow-up schedule in this table, for up to 6 months after the last dose of lumasiran (Section 5.3.1).

^c Demographic data will be obtained from Study ALN-GO1-001.

^d Complete medical history will be obtained at screening and any changes will be updated on admission at the Baseline visit, if different from the Screening visit. Events occurring after signing of the informed consent or assent (if applicable) form and before study drug administration will be captured as medical history.

^e During the Baseline visit and at EOT, height will be measured in triplicate for all patients; for all other study visits height will only be measured for patients <18 years of age. For patients <18 years of age, at each time point, height will be measured in centimeters, and in triplicate, to facilitate calculation of eGFR using the Schwartz Bedside formula.

^f Vital signs (blood pressure, heart rate, body temperature, and respiratory rate) will be measured in the supine or seated position after the patient has rested comfortably for approximately 10 minutes. Body temperature can be measured using oral, tympanic, or axillary methods; the temperature measurement method should be consistently utilized for the study duration, if feasible. At Baseline only, vital signs will be measured within 1 hour predose; and 30 minutes (\pm 5 minutes) and 4 hours (\pm 15 minutes) postdose.

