7.4.8.2. Eliciting and Recording Adverse Events

Eliciting Adverse Events

The patient should be asked about medically relevant changes in his/her health since the last visit. The patient should also be asked if he/she has been hospitalized, had any accidents, used any new medications, or changed concomitant medication routines (both prescription and over-the-counter). In addition to patient observations, AEs will be documented from any clinically relevant laboratory findings, physical examination findings, electrocardiogram changes, or other findings that are relevant to patient safety.

Recording Adverse Events

The Investigator is responsible for recording non-serious AEs that are observed or reported by the patient after administration of the first dose of study drug regardless of their relationship to study drug through the end of study. Non-serious AEs will be followed until the end of study.

The Investigator is responsible for recording SAEs that are observed or reported by the patient after the time when the informed consent is signed regardless of their relationship to study drug through the end of study. SAEs will be followed until satisfactory resolution, until baseline level is reached, or until the SAE is considered by the Investigator to be chronic or the patient is stable, as appropriate.

All AEs must be recorded in the source records for the clinical study center and in the eCRF for the patient, whether or not they are considered to be drug-related. Each AE must be described in detail: onset time and date, description of event, severity, relationship to investigational drug, action taken, and outcome (including time and date of resolution, if applicable).

For SAEs, record the event(s) in the eCRF. If the electronic data capture (EDC) system is unavailable, complete the back-up SAE form.

For AEs that are considered AEs of clinical interest, additional clinical information may be collected based upon the severity or nature of the event. Refer to CRF completion guidelines for details on reporting events in the supplemental eCRF.

For all ISRs, the Investigator, or delegate, should submit an Injection Site Reactions Signs or Symptoms eCRF, recording additional information (eg, descriptions, onset and resolution date, severity, treatment given, and event outcome).

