5.4. Dose Groups

All tables and figures will be presented by the initial dose regimens in this study, unless otherwise specified:

- 1 mg/kg once monthly
- 3 mg/kg once every 3 months
- Pooling of 1 mg/kg once monthly or 3 mg/kg once every 3 months
- 3 mg/kg once monthly
- Total

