A subset of key AE outputs will also be generated to compare study groups of patients initially dosed with 3 mg/kg once monthly versus 3 mg/kg once every 3 months of lumasiran.

Tabulations of the AE data will be adjusted for exposure-time.

Summaries of other Standardised MedDRA Queries (SMQs) or AE groupings may be summarized such as but not limited to the following:

Injection Site Reactions [ISRs]: AEs mapping to the HLT="Injection Site Reactions" using MedDRA dictionary will be included in the summary. Frequency (percentages) of ISRs by HLT and PT will be generated. A separate listing will be generated to display all patients who reported ISRs.

A table will also be generated to display the number of patients with at least 1 ISR, total number of injections, total number of injections complicated by ISRs and corresponding % of injections complicated by ISR with the most common signs and symptoms reported due to ISRs. If there are multiple ISRs that occur in between 2 consecutive injections, then these events will be considered as 1 ISR and considered related to the preceding injection.

Hepatic AEs, including AEs of liver function test (LFT) abnormalities: AEs mapping to the SMQ drug-related hepatic disorders - comprehensive search (includes all narrow and broad terms). Frequency (percentages) of drug-related hepatic disorders will be summarized by SOC and PT. A separate listing will be generated of all patients reporting these events.

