7.3. Exploratory Endpoints

7.3.1. Other Safety Parameters

Additional safety parameters include clinical laboratory parameters (hematology, serum chemistry, LFTs, urinalysis, and coagulations), vital signs, 12-lead ECGs, renal ultrasounds and physical examinations. All additional safety parameters will be analyzed using the Safety Analysis Set.

Clinical Laboratory Parameters: Clinical laboratory parameters will be expressed in SI units. Laboratory data collected and recorded below the LLOQ will be set to the lower limit of quantification for the calculation of summary statistics. Summaries will only include data from the central laboratory (except eGFR as this is summarized in efficacy). Key laboratory parameters will be graded according to NCI CTCAE v5.0.

Laboratory parameters (hematology, chemistry, liver function tests, coagulation and urinalysis), which are continuous variables, will each have a tabular summary of descriptive statistics at each scheduled visit. Descriptive statistics include actual value, change from baseline and percent change from baseline at each scheduled visit.

Shift tables will be generated to summarize shifts from baseline categories to the worst post-baseline categories with directionality specified for any labs which could be reported in either direction (e.g. above threshold or below threshold).

Clinical laboratory tests with normal ranges will be classified as Low, Normal, and High. For these tests, abnormal values will be flagged in the listings with grade appended (e.g. H1 will represent that the lab reported met the threshold of high range with grade 1).

For hematology and chemistry laboratory assessments, summary tables of potentially clinically significant abnormalities will also be provided.

All laboratory data will be presented in data listings. Out of range laboratory results will be identified in listings.

Liver Function Tests (LFTs): A listing will be generated for all patients with abnormal liver function tests as defined by ALT $>3 \times$ ULN, AST $>3 \times$ ULN or total bilirubin $>2 \times$ ULN at any visit.

A tabular summary for LFTs will be generated to summarize the number and associated percentage of patients in each of the categories at any post-baseline visit:

- ALT >1 and ≤ 3 , ALT >3 and ≤ 5 , ALT >5 and ≤ 10 , ALT >10 and ≤ 20 , ALT $>20 \times$ ULN
- AST >1 and ≤ 3 , AST >3 and ≤ 5 , AST >5 and ≤ 10 , AST >10 and ≤ 20 , AST $>20 \times$ ULN

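### Monthly-dosed patients have two safety visits (Months 1 and 2) that every-3-month patients lack, and adjusting for exposure time does not correct by-regimen comparisons of test-detected findings for this

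*SAP*

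**What the plan says.** **Visit schedule.** In Protocol Table 1 the Month 1 (Day 29) and Month 2 (Day 57) columns are headed "For monthly dosing only", and the notes confirm: "Hatched columns indicate study visits to be conducted only for subjects who require monthly dosing". Symptom-directed examination, vital signs and clinical laboratory tests are marked at both visits.

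**How findings become AEs.** Protocol 7.4.8.2 says that "AEs will be documented from any clinically relevant laboratory findings, physical examination findings, electrocardiogram changes, or other findings that are relevant to patient safety". Under Protocol 7.4.8.1, ALT or AST above 3 times ULN is an AE of clinical interest. Protocol 7.4.8.2 also has patients asked at each visit about changes in health since the previous one.

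**Between-regimen comparison.** SAP 7.1.1 says: "A subset of key AE outputs will also be generated to compare study groups of patients initially dosed with 3 mg/kg once monthly versus 3". The other group in this comparison starts on the same dose every 3 months. The adjustment follows: "Tabulations of the AE data will be adjusted for exposure-time".

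**Other safety tables.** SAP 5.4 sets the default display: "All tables and figures will be presented by the initial dose regimens in this study, unless otherwise specified". One of its columns is "Pooling of 1 mg/kg once monthly or 3 mg/kg once every 3 months". SAP 7.3.1 adds: "A tabular summary for LFTs will be generated to summarize the number and associated percentage of patients in each of the categories at any post-baseline" (that is, at any such visit), together with laboratory shifts from baseline to the worst post-baseline category. SAP 5.6 lets unscheduled results count in such categorical summaries.

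Nothing in the SAP limits these summaries to visits that all regimens share, or relates counts to the number of assessments made.

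**The concern.** An any-visit count or a worst value can only rise as more samples are taken. Patients who start on monthly dosing have two more scheduled chances in the first three months for a laboratory, vital-sign or examination abnormality to be seen. If it is judged clinically relevant, it is recorded as an AE. Person-time in the denominator does not remove this, because an extra blood draw adds no person-time.

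The columns are defined by initial regimen, and the starting regimen largely decides who attends Months 1 and 2, so later regimen changes do little to dilute the imbalance. It can also spread: under Protocol 6.2.3.1, a confirmed unexplained transaminase elevation leads to repeat liver tests, and those unscheduled results enter the worst-value summaries.

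Long-term safety is the primary objective, and this is the only between-regimen AE comparison that the SAP names. An excess of test-detected findings under monthly dosing could be read as an effect of dose frequency when part of it comes from the schedule. The relative imbalance is greatest early, and SAP 5.7 plans interim analyses for regulatory use and publication without giving their timing.

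**Working it through.** The documents give no AE rate, event count or group size, so there is no planned figure to reproduce. The check has four steps.

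**1. Does exposure time absorb the imbalance?** SAP 6.5 ends exposure at the earliest of last dose + 84 days, analysis cut-off or end of study. Table 1 puts end of treatment at Day 1428 for everyone, and 1428 + 84 = 1512, the end-of-study day. A completer on either regimen therefore contributes the same person-time, and the adjustment leaves the testing imbalance untouched.

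**2. Scheduled post-baseline laboratory sets (Table 1).** Common visits are Months 3, 6, 9 and 12, then every 6 months from Month 18 to Month 48 (six visits), and Month 54: 4 + 6 + 1 = 11. Monthly dosing adds Months 1 and 2, giving 13.

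| By | Monthly | Every 3 months | Ratio |
|---|---|---|---|
| Month 6 | 4 | 2 | 2.00 |
| Month 12 | 6 | 4 | 1.50 |
| Month 24 | 8 | 6 | 1.33 |
| Month 54 | 13 | 11 | 1.18 |

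Two readings move these counts by one. The Month 3 laboratory mark cannot be placed with certainty in the extracted table; without it the counts are 5 vs 3 and 12 vs 10 at Months 12 and 54. SAP 5.3 takes baseline from the parent study, so the Study 002 Day 1 set may itself be post-baseline; the counts are then 7 vs 5 and 14 vs 12. The difference of two is the same in every case.

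**3. Chance of at least one abnormal value at equal true risk.** With k draws and per-draw probability p, both regimens alike, P(any) = 1 − (1 − p)^k if draws are independent. The values of p are assumptions.

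| p | Month 12 (k = 6 vs 4) | Month 54 (k = 13 vs 11) |
|---|---|---|
| 1% | 5.9% vs 3.9% | 12.2% vs 10.5% |
| 2% | 11.4% vs 7.8% | 23.1% vs 19.9% |
| 5% | 26.5% vs 18.5% | 48.7% vs 43.1% |
| 10% | 46.9% vs 34.4% | 74.6% vs 68.6% |

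For p = 5% and k = 6, 1 − 0.95^6 = 0.265; for k = 4, 1 − 0.95^4 = 0.185.

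Draws from one patient are unlikely to be independent. A beta-binomial with mean 5% and within-patient correlation 0.3 (assumed) gives 15.7% vs 12.7% at Month 12 and 21.8% vs 20.5% at Month 54. At correlation 0.5 it gives 11.7% vs 10.1% and 14.9% vs 14.2%.

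In an assumed group of 10, under independence, the gap is 0.2 to 1.3 patients at Month 12 and 0.2 to 0.6 at Month 54.

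**4. Dependence on how long the abnormality lasts.** Suppose an abnormality lasts L days, with onset uniform over follow-up, and is detected if any scheduled visit falls within it. The ratio of detection probabilities, monthly to every 3 months, is:

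| L (days) | Month 12 | Month 54 |
|---|---|---|
| 28 or less | 1.50 | 1.18 |
| 42 | 1.25 | 1.09 |
| 56 | 1.13 | 1.05 |
| 84 or more | 1.00 | 1.00 |

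An abnormality that lasts 84 days or more is still present at the next common visit, so the extra visits add nothing. If a summary uses common visits only, k is equal (4 and 4, 11 and 11) and the excess from scheduled testing is zero at every p.

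**The case against.** Much can be said against giving this weight.

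- **The named comparison is limited.** SAP 7.1.1 compares a subset of AE outputs. Any-visit liver and shift tables stand side by side only through the default display rule in SAP 5.4. A reader might infer that the SAP formally contrasts any-visit abnormalities between the two 3 mg/kg regimens; it does not.
- **Many AEs are hardly touched.** Patients are asked about events since the last visit, so symptomatic events in Months 1 and 2 can still be reported at Month 3. Only clinically relevant findings become AEs. Injection site reactions also have a per-injection summary. These points stand, and they confine the problem to transient findings detected by testing.
- **Dose differs too.** At 28- and 84-day intervals with no regimen change, there are up to 52 versus 18 doses through end of treatment (1428/28 + 1 and 1428/84 + 1). A reader might infer that an excess under monthly dosing would come from extra testing alone. The documents do not support that: a real effect of more doses would look the same in these tables.
- **Dropping early visits has a price.** Days 29 and 57 are when early transient harm in the more heavily dosed group would be seen. Common visits are not fully like for like either: predose at Day 85, a monthly patient is about 28 days after a dose and an every-3-month patient about 84. This stands, and it is why a common-visit analysis should not replace the full one.
- **Much is already visible.** The SAP plans by-visit laboratory summaries, listings of all laboratory data and by-patient AE listings for at most 20 patients. SAP 5.7 describes the interim analyses as descriptive, and no between-regimen test is specified. That removes concern about a false-positive test, but not the bias in a displayed percentage, and no listing tells the reader that the columns rest on different numbers of assessments.

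**Conclusion.** The point holds in a limited form. The unequal schedule, the by-regimen AE comparison and the by-regimen any-visit tables are all in the documents, and the planned exposure-time adjustment cannot correct the imbalance. Monthly dosing *can* look worse on transient laboratory-, vital-sign- or examination-detected abnormalities at equal true risk. It need not, and an observed excess could equally reflect the larger number of doses; the two cannot be separated from these tables.

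Under independent draws and assumed per-draw rates of 1% to 10%, the artefact is about 2 to 12.5 percentage points at Month 12 and 2 to 6 points at Month 54. At 5% with correlation 0.3 it falls to 3.0 points (15.7 − 12.7) and 1.3 points (21.8 − 20.5). Over the full study it is under one patient in an assumed group of 10. It matters most for early data cuts and short-lived abnormalities.

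These sizes rest on assumed per-draw rates and correlation, no regimen change, and no missed or unscheduled visits. The direction and the difference of two scheduled visits come from Table 1.

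**What to change.** Keep the full-data tables and listings as the main safety presentation. Add to SAP 7.1.1 and 7.3.1:

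- A sensitivity version of the by-regimen any-post-baseline liver test, worst-shift, and potentially clinically significant laboratory and vital-sign tables, limited to visits scheduled for all regimens and therefore without Months 1 and 2.
- In the 3 mg/kg monthly versus every-3-month AE comparison, a flag on AEs first identified from a Month 1 or Month 2 laboratory, vital-sign or examination finding.
- A footnote on the by-regimen tables giving the number of assessments per regimen and stating that Months 1 and 2 are held for monthly dosing only. It should also cover the pooled column, which combines patients on both schedules.

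The sensitivity version should not become the main contrast. It leaves out early findings in monthly-dosed patients and must be read beside the full tables.

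The cost is SAP wording, a few repeat tables and a medical-review flag on AEs. No new visits or samples are needed.

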7.2. Secondary Endpoints

7.2.1. Evaluate the pharmacodynamic effect of lumasiran on urinary oxalate excretion

The analysis of 24-hour urinary oxalate excretion corrected for BSA will be based upon the results that meet the validity criteria (i.e., creatinine excretion ≥ 10 mg/kg, duration of collection 18 to 26 hours, no missing voids and the sample was not collected within 14 days after the most recent dialysis session, if applicable). The analysis will be generated separately based upon data from laboratories using a clinical diagnostic PD assay or quantitative PD assay.

Correlations between the assays will be performed comparing oxalate values, 24-hour urinary oxalate corrected for BSA, change and percentage change of 24-hour urinary oxalate corrected for BSA. Per-patient spaghetti plots may also be generated to compare the results over time.

24-hour urinary oxalate (mmol/24h/1.73m²) corrected for BSA at each visit per patient is calculated as follows:

$$[\text{Urine oxalate concentration (umol/L)/1000 (umol/mmol)}] * [\text{24hr urine volume (mL)/1000 (mL/L)}] * [\text{24 hours/actual collection hours}] * 1.73 / (\text{BSA})$$

where BSA=square root (mean height (cm)*weight (kg)/3600) at the visit.

Data will be summarized descriptively at baseline and at each post-baseline visit. Tabular summaries will include actual value, change from baseline and percent change from baseline at each scheduled visit. Per-patient figures and mean (+/-SEM) plots over time of the actual values, change from baseline and percent change from baseline will be generated. A table of the maximum percent reduction per patient will also be generated.

An analysis of the percentage of time at or below 1.5 x ULN will also be summarized. For each patient, the percentage of time will be calculated as follows:

$$\text{Percentage of time at or below 1.5x ULN} = \frac{\text{cumulative months at or below 1.5 x ULN}}{\text{cumulative months of valid assessments}} * 100$$

where cumulative months at or below 1.5x ULN will be defined as the summation across all intervals that met the threshold of at or below 1.5x ULN and cumulative months of valid assessments will be defined as the summation across all valid post-baseline collections. In order to quantify the months at or below 1.5x ULN, a linear interpolation method will be used to determine the bookend dates at which the patient crossed into the threshold and crossed out of the threshold.

Descriptive statistics of percentage of time at or below 1.5x ULN (among the subset of patients who had at least 1 post-baseline value that was at or below 1.5x ULN) will be presented. In addition, the number of patients and associated percentage of patients in each category (e.g., <25%, 25 to <50%, 50 to <75%, and $\geq 75\%$) will also be presented.

The analysis of the percentage of time will also be calculated using the threshold of at or below ULN.

7.2.2. Change in estimated glomerular filtration rate (eGFR) and measured creatinine clearance over time

Analyses of eGFR and measured creatinine clearance over time will be performed on the Safety Analysis Set.

The eGFR (mL/min/1.73m²) will be calculated from serum creatinine (SCr) based on the Modification of Diet in Renal Disease (MDRD) formula for patients ≥ 18 years of age at enrollment and the Schwartz Bedside Formula for subjects <18 years of age at enrollment in the parent study.

MDRD Formula

- $\text{eGFR (mL/min/1.73m}^2\text{)} = 175 \times (\text{SCr } [\mu\text{mol/dL}] / 88.4)^{-1.154} \times (\text{age})^{-0.203} \times (0.742, \text{ if female}),$
or $\times (1.212, \text{ if African American})$

Schwartz Bedside Formula

- $eGFR (\text{mL/min}/1.73\text{m}^2) = (36.2 \times \text{height [cm]}) / \text{Scr} (\mu\text{mol /dL})$

The eGFR ($\text{mL/min}/1.73 \text{ m}^2$) will be categorized into the following categories: ≥ 90 , 60 to < 90 , 30 to < 60 , 15 to < 30 , and < 15 . A shift table of baseline to worst post-baseline eGFR (i.e., category with the lowest value) will be presented. Additionally, the eGFR will also be summarized descriptively at each scheduled visit. The descriptive statistics will include actual value, change from baseline and percent change from baseline at each scheduled visit. Per-patient plots and mean ($+\text{- SEM}$) plots over time of the actual values, change from baseline and percent change from baseline will be generated. Additionally, slope of change of eGFR over time is will be estimated by a linear mixed effect model, if appropriate.

Analysis of measured creatinine clearance will be performed on the PD Analysis Set. The analysis will include only valid values (note: valid is defined as: creatinine $\geq 10 \text{ mg/kg}$, duration of collection 18 to 26 hours, no missing voids, and the sample was not collected within 14 days after the most recent dialysis session, if applicable).

Measured urine creatinine clearance at each visit per patient will be calculated as:

$$\text{Urine Creatinine concentration (mg/dL)} * 24\text{-hour urine volume (mL)} / \text{plasma creatinine (mg/dL)} * \text{total minutes of collection time} * 1.73 / \text{BSA}$$

where BSA=square root (mean height (cm)*weight (kg)/3600) at that visit.

Tabular summaries will include actual value, change from baseline and percent change from baseline at each scheduled visit.

Per-patient figures and mean ($+\text{-SEM}$) plots over time of the actual values, change from baseline and percent change from baseline will be generated.

